#### 4.6 Withdrawal of Subjects from the Study

The subjects will be informed that they have the right to withdraw from the study on their own accord at any time, for any reason and without having to state their reason and that this will not affect their future management and treatment. When a subject chooses to withdraw from the study, where possible, the Investigator will record a reason according to the following:

- Recovery/no longer experiencing symptoms of HDM allergic rhinoconjunctivitis.
- Lack of therapeutic response.
- Treatment related side effects.
- Unpleasant study procedures.
- Another disease or condition intervenes and prevents continuation in the study.
- External factors unrelated to the study.

**VERSION FINAL 4.0** CONFIDENTIAL **PAGE 29 OF 92**  The subject may also be withdrawn by the Investigator for the following reasons:

DATE 01 APRIL 2015

- Adverse events (AEs), which in the opinion of the Investigator compromises the subject's participation in the study.
- Non-compliance with study procedures.
- Lost to follow-up.
- Withdrawal of consent.
- Protocol violation.
- Termination of the study.
- Pregnancy prior to completion of administration of study medication.
- Deterioration in the subject's signs/symptoms and/or the subject develops a disease or condition prior to completion of administration of study medication that, in the opinion of the Investigator, would compromise the subject's safety in continuing in the study.
- Use of any of the prohibited therapies.

In addition to this list of general criteria for withdrawing subjects from the study dosing should immediately be discontinued (and not restarted) in the event of one or more of the following events:

- A grade 3 or 4 systemic allergic reaction (see Appendix 4)
- Two consecutive doses result in a grade 3 or 4 injection site reaction despite reduction of the dose (See Section 5.5.1)
- A serious adverse event that in the opinion of the Investigator is treatment related
- Medical necessity for a subject to use any of the contraindicated medications (see Section 5.8.5) during the treatment period.

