Treatment discontinuation will not necessarily result in withdrawal of the subject from the study. For the subjects who withdraw from the study, all safety assessments scheduled for the Period 3 Follow-Up (Visit 5) (see Section 6.2.3.2) will be requested and observations will be recorded as far as is possible. Reasons for omission of tests will be documented. The date and reason(s), if provided, for withdrawal from the study will also be recorded in the electronic Case Report Form (eCRF).

If the subject withdraws due to an AE, all of the Period 3 Follow-Up (Visit 5) assessments will be requested and the event followed until resolution or care is transferred to the subject's primary care physician or a specialist.

VERSION FINAL 4.0 CONFIDENTIAL PAGE 30 OF 92

Subjects who are withdrawn may be replaced.

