# 7.5.4 Safety Analysis

Safety will be evaluated by analysis of the following parameters:

- AEs;
- Physical examination;
- Clinical laboratory tests (including immunology);
- FEV1;
- Vital signs;
- Local reactions at the injection site.

The primary safety endpoint will be a comparison of the number of adverse events, and subjects with adverse events, in the HDM-SPIRE groups compared to placebo.

For safety analysis, descriptive statistics such as N, mean, median, minimum, maximum and SD will be summarised by treatment group for continuous variables. Frequency distribution will be summarised for categorical variables. No formal inferential tests will be performed on safety data.

The number and percentage of subjects who experience AEs will be presented by treatment group. Based on the MedDRA Preferred Term, subjects who experience the same AE on multiple occasions will be summarised at the maximum severity and most conservative relationship to the study medication. If 2 or more AEs are reported as a single event, the

VERSION FINAL4.0 CONFIDENTIAL PAGE 74 OF 92

individual terms will be reported as separate AEs.

The total number of AEs will be summarised by MedDRA System Organ Class and Preferred Term for each treatment group. Descriptive statistics will be presented for differences between the HDM-SPIRE treatment groups and the placebo group, but no hypothesis testing is planned.

Any deaths, SAEs and AEs leading to discontinuation of study medication administration will also be summarised by treatment group.

Local reactions at the injection site will be summarised by type of reaction and visit for each treatment group.

Physical examinations data will be listed only.

Vital signs will be presented as descriptive statistics on absolute values and the change from baseline will be summarised for each treatment group by visit.

 $FEV_1$  will be presented as descriptive statistics and the absolute change from baseline and percentage change from baseline will be summarised for each treatment group by visit.

Clinical laboratory data for individual subjects will be listed and any out of range values will be highlighted. Laboratory data will be summarised for each treatment group by visit as follows: summary of absolute values and change from baseline and analysis of shifts from baseline.

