## 9. DISPOSITION AND WITHDRAWALS

Disposition and withdrawals are to be summarised for the ENR population.

Additionally, disposition and withdrawal summaries are to be presented for the following subgroups:

- Asthma status (Absent/Present/Missing) as captured on the Randomization eCRF (RAND)
  - Where Controlled and Partly/Uncontrolled are categorised as Present and
  - No Asthma is categorised as Absent
- TRSS categorised as TRSS  $< 16$ , TRSS  $\geq 16$  or Missing as captured on the Randomization eCRF (RAND)

The frequency (n) and percentage (%) of the following disposition and withdrawal categories are to be reported:

- Subjects screened
- Screen failures, defined as subjects where the Study Entry eCRF completed at the Screening visit indicates screening was not passed

---

Document: TH005 SAP Version 2.docx  
Author: [name]

Version Number: 2.0  
Version Date: 24MAR2017

Template No: CS\_TP\_BS016 – Revision 3  
Effective Date: 01May2012

Reference: CS\_WI\_BS005

Copyright © 2012 Quintiles Transnational Corp. All rights reserved.  
The contents of this document are confidential and proprietary to Quintiles Transnational Corp. Unauthorized use, disclosure or reproduction is strictly prohibited.

- Subjects that initially failed Screening may have been re-screened for eligibility following modifications to eligibility criteria in protocol amendments. Re-screened subjects are to be provided with a new Screening number and a link to the previous Screening number is to be captured on the Rescreening Status eCRF. Rescreened subjects that pass Screening are not to be counted as screen failures under their previous Screening numbers and are only to be accounted for once using the newly assigned Screening number and status.
- BAE failures, defined as subjects where the Study Entry eCRF (SENTRY) completed at the end of the BAE period indicates that the BAE period was not passed
- Randomised subjects, as indicated on the Randomisation eCRF (RAND). Subjects are to be eligible for randomisation if they passed both Screening as well as BAE.
- Completed study medication, early withdrawal from treatment period as well as primary reason for termination of study medication as entered on the End of Treatment eCRF (EOT)
  - Completed study medication is defined as receiving 8 doses of study medication from Visit 3A to Visit 3H

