- Completed the study, early withdrawal from the study as well as primary reason for early withdrawal from the study as entered on the End of Study eCRF (EOS)

Completed the study is defined as completing the Follow-up Period (Visit 5) without prior early withdrawal from the study as indicated on the End of Study eCRF (EOS), regardless of completion of study medication as indicated on the End of Treatment eCRF (EOT). The frequency (n) and percentage (%) of subjects assigned to each analysis population is to be provided for the Randomized, ITT, PP and SAF populations, as well the reasons for exclusion from each population.

Percentages are to be calculated relative to the total number of subjects in the analysis population.

The following listings are planned for presentation:

- Subjects screening status (ENR population)
  - Includes eligibility criteria and inclusion/exclusion criteria exceptions
- Subject disposition (RND population)
- Analysis population assignment (ENR population)
- Major protocol deviations (RND population)

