**16.1.5. TEAES LEADING TO PREMATURE STUDY OR TREATMENT DISCONTINUATION**

Treatment-emergent AEs leading to premature study discontinuation are to be identified as TEAES where the Outcome on the Adverse Events Detail eCRF (AEDT) is indicated as "Subject withdrawn because of this event".

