**16.1.6. TREATMENT RELATED TEAES LEADING TO PREMATURE TREATMENT DISCONTINUATION**

Treatment related TEAES leading to premature treatment discontinuation are to be identified as TEAES where the Outcome on the Adverse Events Detail eCRF (AEDT) is indicated as "Subject withdrawn because of this event" and the Causality is indicated as "Related" and the primary reason for treatment termination on the End of Treatment eCRF (EOT) is indicated "Adverse Event".

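### SAP 16.1.5 and 16.1.6 use one AE outcome value to identify both leaving the study and stopping treatment, so at least one of the two discontinuation tables can misclassify events

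*SAP*

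**What the plan says.** **Protocol.** Section 4.6 separates stopping dosing from leaving the study. It says "dosing should immediately be discontinued (and not restarted) in the event of one or more of the following events", and the first event listed is "A grade 3 or 4 systemic allergic reaction (see Appendix 4"). A serious adverse event that the investigator considers treatment related is also listed. The same section then states: "Treatment discontinuation will not necessarily result in withdrawal of the subject from the study". Section 7.5.4 commits to a table: "Any deaths, SAEs and AEs leading to discontinuation of study medication administration will also be summarised by treatment group". That commitment has no causality restriction.

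**SAP, adverse events.** The heading of 16.1.5 covers study or treatment discontinuation, but its only rule is for the study: "Treatment-emergent AEs leading to premature study discontinuation are to be identified as TEAES where the Outcome on the Adverse Events Detail eCRF (AEDT") is the value saying that the subject was withdrawn because of the event. Section 16.1.6 concerns treatment: "Treatment related TEAES leading to premature treatment discontinuation are to be identified as TEAES where the Outcome" is that same value, and in addition the causality is Related and the primary reason on the End of Treatment form is Adverse Event. All three conditions must hold.

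**SAP, disposition.** Section 9 keeps the two concepts apart. It defines study completion "regardless of completion of study medication as indicated on the End of Treatment eCRF (EOT"), and it separately tabulates "early withdrawal from treatment period as well as primary reason for termination of study medication as entered on the End of Treatment eCRF (EOT").

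**The concern.** A subject can follow the protocol exactly by having a reaction that ends dosing, recovering, and completing all three PAC periods. The AE discontinuation tables should show that event as stopping treatment and not as ending study participation. With a single outcome value behind both tables, the SAP has no way to record this combination.

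This matters because the study is meant to choose a dose and regimen for Phase 3 (protocol 2.0), and 20 nmol is above the highest unit dose evaluated before (protocol 1.3.1). Which events stopped dosing, by arm, is a main tolerability input to that choice. Section 9 gives the number of subjects who stopped for an adverse event, but not the event term or its causality. As written, the section 9 count and the 16.1.6 count can disagree, and the SAP has no rule for reconciling them.

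**Working it through.** The plan states no figure to reproduce. The check applies the two SAP rules, as worded, to the situations the protocol allows. 'Withdrawn' below means the outcome value that both rules use.

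| Situation | Outcome recorded | In 16.1.5 (study)? | In 16.1.6 (treatment, related)? | Correct placement |
|---|---|---|---|---|
| 1. Related TEAE stops dosing; subject leaves the study because of it | Withdrawn | Yes | Yes | Both |
| 2. Related TEAE stops dosing; subject stays | Recovered, ongoing, etc. | No | No | Treatment only |
| 3. As 2, but the site uses the value for a dosing stop | Withdrawn | Yes | Yes | Treatment only |
| 4. Unrelated event A stops dosing; subject stays, then leaves because of related event B | A: recovered; B: withdrawn | B | B | A: treatment, any causality; B: study only |
| 5. Unrelated TEAE stops dosing; subject stays | Recovered | No | No (not related) | Treatment, any causality |

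Reading the rows:

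- Row 1 is the only one where both tables are right.
- Rows 2 and 3 are the same clinical event under two readings of the field. Row 2 omits it from both tables. Row 3 puts a subject who stayed into the study-discontinuation table. No reading of the value makes both tables right.
- Row 4 arises because 16.1.6 joins an event-level outcome to a subject-level End of Treatment reason and does not require them to refer to the same event. Event B is counted as stopping treatment although it did not.
- Row 5 shows the gap against protocol 7.5.4. No SAP rule identifies treatment-stopping TEAEs of any causality. If sites marked such events as withdrawn they would enter 16.1.5, but labelled as study discontinuations and mixed with them.

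Two related details. The five outcomes listed in protocol 6.4.1 (recovered, recovered with sequelae, ongoing, death, unknown) do not include a withdrawn value. If the eCRF field allows only one choice, a resolved reaction could not also be marked withdrawn. And SAP 16.1.1.2 treats missing causality as Related, whereas 16.1.6 asks for Related to be indicated.

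**Illustration only.** The documents give no event rates, so every rate here is assumed. Let p be the true rate of related AEs that stop dosing, and r the share of those subjects who stay, equal across arms. There are 165 subjects per arm.

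Under the row 2 reading, and ignoring row 4, the counted rate is p(1 − r). With p = 1% on placebo and 4% on active:

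- r = 0: 165 × 0.01 = 1.65 against 165 × 0.04 = 6.60 subjects; difference 3.00 points.
- r = 25%: 1.24 against 4.95; 2.25 points.
- r = 50%: 0.83 against 3.30; 1.50 points.
- r = 75%: 0.41 against 1.65; 0.75 points.

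With p = 0.5% and 2%, the difference goes from 1.50 to 1.12, 0.75 and 0.38 points.

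Under the row 3 reading, 16.1.6 keeps all of these events, and 16.1.5 gains 165 × p × r subjects who did not leave. At p = 4% and r = 50% that is 165 × 0.04 × 0.50 = 3.3 in an active arm.

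**The case against.** The strongest reply is that the eCRF is not in the documents and the outcome value does not say what the subject was withdrawn from. The 16.1.5 heading names both kinds of discontinuation, the overview row in SAP 16.1 does too, and 16.1.6 adds an End of Treatment condition. That fits an intention in which the value marks an event causing either kind of withdrawal and the End of Treatment form then selects the treatment stops. On that reading 16.1.6 does not lose the events of row 2. This stands: omission is possible, not established. It does not rescue the pair of rules, because the body of 16.1.5 assigns the same value to study discontinuation, and row 4 can occur on either reading.

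A reader might infer that severe reactions would disappear from the report. The documents do not support that. A systemic allergic reaction is an event of special interest with its own table (SAP 16.1.7), related and serious events are tabulated, and section 9 still counts the subject as stopping treatment for an adverse event. A reader might also infer that the rule can only undercount, and so must shrink the excess on active. That does not follow either: row 3 overcounts 16.1.5 and row 4 adds an event to 16.1.6 that did not stop dosing.

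Some stopping routes are unaffected, because the protocol withdraws the subject from the study: two consecutive half doses not tolerated (5.5.1), and contraindicated medication in Period 2 (5.8.5). The output templates were not available either, so what a listing might show beside an event is unknown.

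**Conclusion.** The point holds as a defect in two table definitions. One outcome value is asked to identify two events that the protocol and SAP section 9 treat as different. 16.1.6 does not tie the event to the End of Treatment reason, and the any-causality summary promised in protocol 7.5.4 has no rule behind it.

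The direction of any error depends on how sites used the outcome field, and its size cannot be determined from the documents. The illustrative figures rest on assumed rates and an equal staying share in each arm. If no subject stops dosing for an adverse event and stays, rows 2, 3 and 5 are empty and row 4 cannot arise. Safety is descriptive, so no test or efficacy result is affected. It is worth correcting before unblinding because the tables inform the choice of regimen and the correction is cheap.

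**What to change.** Replace 16.1.5 and 16.1.6 with three definitions, and align the overview rows in 16.1:

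- **(a) TEAEs leading to premature study discontinuation:** the subject-withdrawn outcome value, together with early withdrawal on the End of Study eCRF.
- **(b) TEAEs leading to premature treatment discontinuation, any causality:** in subjects whose primary End of Treatment reason is Adverse Event, the TEAE or TEAEs for which study medication was stopped, whether or not the subject stayed in the study. Identify the event from the action-taken entry and agree it at the blind data review.
- **(c) Treatment-related subset:** events in (b) with causality Related or missing, matching 16.1.1.2.

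Add a statement that the number of subjects in (b) is reconciled with the End of Treatment count in section 9.

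No new assessments are needed. Because action taken is recorded only as a brief description (protocol 6.4.1), linking events to End of Treatment records may be manual. It is confined to subjects who stopped treatment for an adverse event and can be done blinded at a review already planned.

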**16.1.7. TEAES OF SPECIAL INTEREST**

TEAES of special interest are defined as TEAES for which "Adverse Event of Special Interest (AESI)" is indicated as "Yes" on the Adverse Events Detail eCRF (AEDT).

**16.1.8. TEAES WITHIN 24 HOURS OF ANY DOSE**

TEAES within 24 Hours of any dose are defined as any AE that has a start date within 24 Hours of any dose, not only the first study drug administration date and time. If the AE onset time is missing and the start date of the TEAE is on or one day after any dosing date, the AE is to be assumed to have occurred within 24 hours of the dose.

---

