# 1.3 Justification for Key Elements of the Study Design

### 1.3.1 Dose Selection

Three active dose regimes will be evaluated in this study. The doses have been selected on the basis of data from Study TH002 (see Section 1.2). In this study a unit dose of 12 nmol was found to be more effective than unit doses of 3 and 6 nmol whilst being equally well tolerated with no safety concerns. However, the data on the 12 nmol unit dose was not unequivocal in that subjects who received 4 administrations responded well, as did subjects in Phase 1 of the study who received 11 administrations of this dose. However, subjects in Phase 2 of the study who received 11 administrations of 12 nmol did not respond better than subjects who received placebo. *Post-hoc* analyses suggested that this lack of effect may have been due to differential responses according to symptom severity at baseline, together with greater than expected data variability, however it was not possible to refute conclusively the hypothesis that additional doses (over and above 4 doses) negated the beneficial effects of the 4 dose regimen.

The highest unit dose of HDM-SPIRE evaluated in any study is 12 nmol and in Study TH002 a regimen of four administrations of this dose was found to be effective. It is not known whether higher unit doses will be more effective and/or safe and well tolerated.

The rationale for each dose regimen of HDM-SPIRE in the TH005 study is, therefore, as follows:

Dose	Dose Regimen	Rationale
Group		
1	8 x placebo 4 weeks apart	Control group
2	4 x 12 nmol HDM-SPIRE followed by 4 x placebo 4 weeks apart	To confirm the efficacy of this dosing regimen that was observed in study TH002
3	4 x 12 nmol HDM-SPIRE 4 weeks apart followed by a second course of 4 x 12 nmol HDM-SPIRE 4 weeks apart	To determine whether a second course of 4 doses of HDM-SPIRE negates the efficacy of the first course, and To determine whether two courses of HDM-SPIRE are more effective than one course

VERSION FINAL 4.0 CONFIDENTIAL PAGE 18 OF 92

by 4 x placebo 4 weeks apart

4 x 20 nmol HDM-SPIRE followed To determine whether a higher (than 12 nmol) unit dose has greater efficacy and equivalent safety/tolerability

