## 3. STUDY DESIGN

### 3.1. GENERAL DESCRIPTION

This is a randomised, double-blind, placebo-controlled, parallel group, multi-centre field assessment of three dose regimens of HDM-SPIRE administered at 4 weekly intervals for 28 weeks.

Document: TH005 SAP Version 2.docx

Author: [name]

Version Number:

2.0

Version Date:

24MAR2017

Template No: CS\_TP\_BS016 – Revision 3

Effective Date: 01May2012

Reference: CS\_WI\_BS005

Copyright © 2012 Quintiles Transnational Corp. All rights reserved.

The contents of this document are confidential and proprietary to Quintiles Transnational Corp. Unauthorized use, disclosure or reproduction is strictly prohibited.

A total of approximately 660 subjects are to be randomised into the study, with approximately 165 subjects in each of the three HDM-SPIRE treatment groups and 165 in the placebo group.

Subjects are to attend the investigative centre for screening. Subjects meeting the inclusion/exclusion criteria are to be randomised to either one of the following three active treatment groups or the placebo group in a 1:1:1:1 ratio:

- 8 x placebo, 4 weeks apart (placebo)
- 4 x 12 nmol HDM-SPIRE followed by 4 x placebo, 4 weeks apart
- 4 x 20 nmol HDM-SPIRE followed by 4 x placebo, 4 weeks apart
- 8 x 12 nmol HDM-SPIRE 4 weeks apart

Following randomisation a total of 8 doses of HDM-SPIRE or placebo are to be administered at the investigative centre, one dose every 4 weeks ( $\pm 2$  days), for a total duration of 28 weeks as shown in the Table 1 below:

Table 1: Dosing Schedule								
Visit	3A	3B	3C	3D	3E	3F	3G	3H
Week ( $\pm 2$ days)	0	4	8	12	16	20	24	28
Treatment Group								
Placebo	P	P	P	P	P	P	P	P
HDM-SPIRE 4 x 12 nmol	X	X	X	X	P	P	P	P
HDM-SPIRE 4 x 20 nmol	X	X	X	X	P	P	P	P
HDM-SPIRE 8 x 12 nmol	X	X	X	X	X	X	X	X

X = HDM-SPIRE doses, P = Placebo doses.

Subjects are to complete an electronic diary (eDiary) during the following four periods for efficacy evaluation:

- Baseline allergy evaluation (BAE)

Subjects are to record Baseline Rhinoconjunctivitis symptom scores (RSS) and rescue medication score (RMS) in an eDiary during a period of approximately 3 weeks prior to randomisation.

The RSS and RMS assigned to the BAE period for a subject is to be taken as all scores entered on the subject's eDiary dated from the date of Visit 2A up to and including the date of Visit 2B.

- Post-administration collection period 1 (PAC1)

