## **14. STUDY MEDICATION COMPLIANCE**

Compliance to study medication is to be presented for the ITT population.

Compliance to study medication is to be summarised by descriptive statistics and treatment group for

- Compliance over first 4 doses (Visit 3A to Visit 3D)
- Compliance over last 4 doses (Visit 3E to Visit 3H)
- Overall compliance (Visit 3A to Visit 3H)

---

Document: TH005 SAP Version 2.docx

Author: [name]

Version Number:

2.0

Version Date:

24MAR2017

Template No: CS\_TP\_BS016 – Revision 3

Effective Date: 01May2012

Reference: CS\_WI\_BS005

Copyright © 2012 Quintiles Transnational Corp. All rights reserved.

The contents of this document are confidential and proprietary to Quintiles Transnational Corp. Unauthorized use, disclosure or reproduction is strictly prohibited.

---

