### 16.1. ADVERSE EVENTS

An AE is defined as any untoward medical occurrence in a subject administered study treatment that does not necessarily have a causal relationship with the treatment. An AE can therefore be any unfavourable and unintended sign (i.e. an abnormal laboratory finding), symptom (i.e., rash, pain, discomfort, fever, dizziness, etc.), disease (i.e., peritonitis, bacteraemia, etc.) or outcome of death temporally associated with the use of study treatment, whether or not considered causally related to the study medication.

Adverse Events (AEs) are to be coded using MedDRA Version 19.0.

Adverse events are to be classified as either pre-treatment AEs or treatment-emergent adverse events (TEAEs) based on the start date of the event as follows:

- Pre-treatment AEs: Defined as any AE which started or worsened on or after informed consent and before study medication administration
- TEAE: Defined as any AE which started or worsened on or after first study medication administration.

See Appendix 2 for handling of partial dates for AEs. In the case where it is not possible to define an AE as treatment-emergent or not, the AE is to be classified as the worst case; i.e. treatment-emergent.

An overview of the frequency (n) and percentage (%) of subjects is to be provided for the following TEAEs together with the actual number of mentions (m) of the event per category:

- Any TEAE
- Serious TEAEs
- TEAEs leading to death

---

Document: TH005 SAP Version 2.docx

Author: [name]

Version Number:

2.0

Version Date:

24MAR2017

Template No: CS\_TP\_BS016 – Revision 3

Effective Date: 01May2012

Reference: CS\_WI\_BS005

Copyright © 2012 Quintiles Transnational Corp. All rights reserved.

The contents of this document are confidential and proprietary to Quintiles Transnational Corp. Unauthorized use, disclosure or reproduction is strictly prohibited.

---

- Life-threatening TEAEs
- TEAEs leading to premature study and treatment discontinuation
- Treatment related TEAEs leading to premature treatment discontinuation
- Severe TEAEs
- TEAEs related to study medication
- TEAEs of special interest
- TEAEs within 24 hours of any dose of study medication

In addition to the overview of TEAEs, incidence of all TEAEs in the sub-sections below is to be presented by System Organ Class (SOC) and Preferred Term (PT). If an AE occurs more than once the subject is to be counted once per SOC and PT as relevant.

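### The TEAE, special-interest and 24-hour summaries pool active injections 1-4 with placebo injections 5-8 in the two four-dose arms; a descriptive split by dosing phase should be added

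*SAP*

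**What the plan says.** Protocol 1.3.1 gives the reason for the 20 nmol arm: "To determine whether a higher (than 12 nmol) unit dose has greater efficacy and equivalent safety/tolerability". The same section says that 12 nmol is the highest unit dose tested so far.

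SAP 3.1 describes this arm as "4 x 20 nmol HDM-SPIRE followed by 4 x placebo, 4 weeks apart", and the 4 x 12 nmol arm has the same pattern. The dosing table puts the active injections at Visits 3A-3D (weeks 0-12) and the placebo injections at Visits 3E-3H (weeks 16-28). Placebo injections count as doses: "a total of 8 doses of HDM-SPIRE or placebo are to be administered at the investigative centre".

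SAP 16.1 takes a TEAE to be: "Defined as any AE which started or worsened on or after first study medication administration". The overview shows subjects and number of mentions. The detailed tables are by system organ class and preferred term, with each subject counted once. SAP 16.1.8 forms the 24-hour set from "any AE that has a start date within 24 Hours of any dose, not only the first study drug administration date and time". An event with no onset time, dated on the dosing day or the day after, is also assigned to the dose. Nothing in SAP 16.1, including related TEAEs (16.1.1.2) and events of special interest (16.1.7), is divided by visit, dosing phase or content of the injection. Protocol 7.5.4 also presents AEs by treatment group only.

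Other parts of the SAP do make the distinction. Compliance is split into Visits 3A-3D and 3E-3H (SAP 14). Local reactions are shown by grade and visit (16.7.2). FEV1 (16.7.1) and vital signs (16.5) are shown as change from pre-dose to 30 minutes post-dose at each dosing visit.

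**The concern.** The question about 20 nmol concerns a unit dose, whereas the planned TEAE tables describe a regimen. In the two four-dose arms, half of the injections that can place a subject in the 24-hour table are placebo. A subject whose only event follows injection 6 counts in the 20 nmol column in the same way as a subject whose event follows injection 2. If placebo injections carry any background of events, the percentages in the active and placebo arms move closer together.

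A second problem arises when 4 x 20 is read beside 8 x 12 nmol. The first arm has four active injections and the second has eight, so a higher risk per injection in one can be offset by more active injections in the other.

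Protocol 2.0 says the trial is to identify a dose and regimen for Phase 3. A unit-dose difference in systemic or delayed events that is muted in these tables would therefore bear on that choice.

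**Working it through.** **Figures in the plan.** The documents give no AE rate and no safety precision target, so there is no safety figure to reproduce. The one computable design figure, 150 per arm for 80% power (difference 0.32, SD 0.986, two-sided 5%), does reproduce, but it concerns efficacy and this point does not rest on it.

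**Inputs from the documents.** About 165 subjects per arm and 8 injections each (SAP 3.1); 4 active then 4 placebo in the two four-dose arms.

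**Inputs assumed.** Per-injection risk of an event within 24 hours: q after placebo, a after active. Risks are taken as independent and constant across injections, with every subject receiving all eight. Stopping and dose reduction (Protocol 4.6 and 5.5.1) are ignored.

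**Step 1, planned injections in the 4 x 20 nmol arm.** 165 x 8 = 1,320, of which 165 x 4 = 660 (50%) are placebo.

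**Step 2, percentage of subjects with an event.**
- Doses 1-4: 1-(1-a)^4 active, 1-(1-q)^4 placebo.
- Any of 8 doses: 1-(1-a)^4(1-q)^4 active, 1-(1-q)^8 placebo.
- Subtracting, RD(any dose) = (1-q)^4 x RD(doses 1-4).

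Differences below are taken before rounding.

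| q | a | Doses 1-4, active v placebo | RD (points) | RR | Any of 8, active v placebo | RD (points) | RR | RD kept |
|---|---|---|---|---|---|---|---|---|
| 1% | 2% | 7.8% v 3.9% | 3.8 | 1.97 | 11.4% v 7.7% | 3.7 | 1.48 | 96.1% |
| 2% | 4% | 15.1% v 7.8% | 7.3 | 1.94 | 21.7% v 14.9% | 6.7 | 1.45 | 92.2% |
| 5% | 10% | 34.4% v 18.5% | 15.8 | 1.85 | 46.6% v 33.7% | 12.9 | 1.38 | 81.5% |
| 10% | 20% | 59.0% v 34.4% | 24.6 | 1.72 | 73.1% v 57.0% | 16.2 | 1.28 | 65.6% |
| 20% | 40% | 87.0% v 59.0% | 28.0 | 1.47 | 94.7% v 83.2% | 11.5 | 1.14 | 41.0% |

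At q = 0 nothing is lost.

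**Step 3, event mentions.** The expected excess per subject is 4a - 4q over doses 1-4 and (4a + 4q) - 8q = 4(a-q) over all eight, so it is the same. At q = 5% and a = 10% the excess is 0.20 per subject either way. The ratio still falls, from 0.40/0.20 = 2.0 to 0.60/0.40 = 1.5.

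**Step 4, 20 nmol against 12 nmol.** Assume q = 5%, 10% after 12 nmol and 15% after 20 nmol.
- Doses 1-4: 1-0.85^4 = 47.8% for 20 nmol; 1-0.90^4 = 34.4% for 12 nmol.
- Any dose, 4 x 20: 1-0.85^4 x 0.95^4 = 57.5%.
- Any dose, 8 x 12: 1-0.90^8 = 57.0%.
- Any dose, 4 x 12: 1-0.90^4 x 0.95^4 = 46.6%.

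Beside 8 x 12, the difference of 13.4 points over doses 1-4 becomes 0.5 points. Beside 4 x 12 it becomes 10.9 points, which is the same factor 0.815.

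**The case against.** The strongest reply is that the randomised arms are regimens, that Protocol 7.5.4 makes AEs by group against placebo the primary safety endpoint, and that the SAP tabulates exactly that, descriptively. This stands. The all-dose tables are correct for their purpose, and what is missing is a breakdown.

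A reader might infer that the per-dose safety of 20 nmol is diluted throughout, or that the safety of a second 12 nmol course is hidden. The documents do not support either reading. Local reactions, FEV1 and vital signs are summarised at each dosing visit, so active and placebo injections stay apart in them, and doses 5-8 of 12 nmol can be set against placebo at the same visits. Those measures do not cover everything, however. On dosing days they are taken before and 30 minutes after injection (Protocol Table 6), and subjects may leave after 30 minutes (Protocol 6.2.2.1). Systemic and other events that start later reach the summaries through the TEAE tables.

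A reader might also infer that 20 nmol is never compared fairly with 12 nmol. In fact 4 x 12 against 4 x 20 is like for like, because both arms switch to placebo at the same visit. That contrast is attenuated, not confounded. The mixing with number of active injections arises only beside 8 x 12.

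The size can be overstated in two ways. Part of the fall in the risk ratio is accumulation over more injections: at q = 5% and a = 10%, eight active injections would give 57.0/33.7 = 1.69, so 0.16 of the 0.47 fall from 1.85 to 1.38 would occur with no placebo injections at all. And weeks 0-16 being 16/52 = 31% of follow-up is a share of calendar time, which does not measure dilution.

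Finally, the output templates (SAP 8) and the separate DSMC SAP (SAP 4.1) were not available, so a split there cannot be excluded. Listings carry study day from first dose (SAP 6.1), so individual events can be placed by hand.

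**Conclusion.** The concern holds for the TEAE-based summaries only: all TEAEs, related TEAEs, events of special interest and the 24-hour table. As written, the SAP pools active and placebo injections in the two four-dose arms, and this weakens the subject-level answer to the unit-dose question in Protocol 1.3.1.

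The size depends on the background rate after placebo injections, which the documents do not give. With independent, constant risks, the loss of risk difference is about 4% at q = 1%, 18.5% at 5% and 34% at 10%, and none at zero. The direction is towards no difference from placebo whenever q is above zero. The rule for events without an onset time can only raise q. Excess mentions are preserved in expectation, but SAP 16.1 specifies mentions only for the overview.

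It would go too far to call the planned tables invalid. The change should be made because it improves the answer to one of the trial's own questions at little cost, not because the existing analysis is wrong.

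**What to change.** Keep the all-dose tables. In SAP 16.1, 16.1.1.2, 16.1.7 and 16.1.8, add descriptive summaries of TEAEs, related TEAEs, events of special interest and 24-hour TEAEs for two phases:
- injections 1-4, from Visit 3A to before Visit 3E;
- injections 5-8, from Visit 3E to Visit 3I.

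Show each phase against the placebo arm in the same interval, and assign each 24-hour event to the injection that precedes it. The denominator should be subjects who received at least one injection in that phase. The SAP should also say where the first interval ends for a subject with no Visit 3E injection.

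The injections 5-8 tables need a footnote. Protocol 4.6 stops dosing after certain reactions, so those tables compare subjects who continued and not the full randomised groups. When the by-visit local-reaction tables are read alongside, the pre-dose examination at Visit 3E concerns the Visit 3D site (Protocol 6.4.4.6) and belongs to the first phase.

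A pooled 12 nmol column for injections 1-4 is optional. The two 12 nmol arms have the same schedule up to Visit 3E, so it would rest on about 2 x 165 = 330 subjects.

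The cost is SAP wording and a few more descriptive tables. The dates are already collected, the split is already used for compliance, and no hypothesis tests are added.
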